Basierend auf den Daten der Dialysis Outcomes and Practice Patterns Studie (DOPPS, o.a. Referenz) erscheint die Hypothese der CNI Missklassifikation und verzögerten CNI Progression bei Frauen unwahrscheinlich. So vermuten wir eher psychosoziale bzw. sozioökonomische Hintergründe als Ursache für die Unterrepräsentanz der Frauen an nephrologischen Ambulanzen und bei Nierenersatztherapien.

Die Ziele der vorliegenden Studie sind die Darstellung geschlechtsspezifischer Unterschiede in der Population mit Nierenersatztherapie in Österreich, die Analyse geschlechtsspezifischer Unterschiede bei Therapie und Outcomes von hospitalisierten Patienten mit CNI und die Darstellung der Entscheidungsfindung betreffend der Einleitung eines Nierenersatzverfahrens.

Die Studie wurde in 3 Substudien unterteilt, bestehend aus einer nationalen und einer lokalen retrospektiven Datenanalyse sowie einer Fragenbogenstudie:

1) Darstellung und Analyse geschlechtsspezifischer Unterschiede von Hämodialysepatienten und Hämodialyse assoziierter Mortalität in Österreich

Methode: Abfrage epidemiologischer, klinischer und Hämodialyse-spezifischer Daten aller Patienten aus dem österreichischen Dialyseregister (1965-2015).

2) Erfassung geschlechtsspezifischer Unterschiede in Behandlung und Outcome von hospitalisierten Patienten im Krankenanstaltsverbund mit eingeschränkter Nierenfunktion.

Methode: Geschlechtsspezifische Erfassung aller Patienten, welche mit einer GFR < 60 mL/min/1.73m² im Jahr 2015 auf einer internistischen Abteilung des Krankenanstaltsverbundes hospitalisiert wurden und deren Outcomes (Hospitalisierungsdauer, Mortalität während der Hospitalisierung, Dialyseinitiierung).

3) Darstellung geschlechterspezifischer Unterschiede in der Entscheidungsfindung der Patienten mit terminaler Niereninsuffizienz und der betreuenden Ärzte bezüglich der Einleitung einer Nierenersatztherapie.

Methode: Anonymisierter Patientenfragenbogen für Patienten und Ärzte Team an nephrologischen Ambulanzen. Adressiert werden alle nephrologischen Ambulanzen Österreichs.

TABLE OF CONTENTS

1. INTRODUCTION.....	6
1.1 Women are under-represented in the dialysis population	6
1.2 The under-representation of women in the dialysis population runs counter to their possibly higher prevalence of chronic kidney disease prevalence.....	7
1.3 Women could be under-represented in chronic kidney disease clinics.....	8

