the hemodialysis population will be compared with that of the Austrian general population. Adjusted hazard ratios for the male-to-female mortality risk in hemodialysis patients, by region will be performed using Cox regression analysis. Statistical modeling will closely follow a previously published study of hemodialysis data, analyzed by sex and country/region.⁴ All obtained p-values will be considered exploratory in nature.

2.2 Description and analysis of sex-specific differences in treatment and outcomes in patients with chronic kidney disease.

Hypothesis:

There are sex-specific differences in treatment, length of hospitalization, mortality and dialysis initiation in patients with chronic kidney disease admitted to internal medicine wards.

Methodology:

Patients hospitalized at internal medicine wards of the Krankenanstaltsverbund (KAV) between Jan 1st 2015 and Dec 31st 2015 with eGFR <60 mL/min/1.73m will be included.

Primary study endpoints are length of hospital stay, death within hospitalization and dialysis initiation. Secondary endpoints are renal function parameters (eGFR, serum creatinine, blood urea nitrogen) and proteinuria during hospital stay. Laboratory data will be extracted from the KAV laboratory database and patient characteristics will be derived from the KAV patient management database.

Statistics:

Descriptive statistics will be used for presentation of demographic and clinical patient characteristics and prevalence of chronic kidney disease in women as compared to men.

Further statistical methods will be chosen according to data availability and quality: The present plans include logistic regression to calculate the male-to-female odds of reaching one of the endpoints, conditional logistic regression for pair-matched data or logistic regression with propensity scoring.

2.3 Descriptive analysis of decision-making by doctors and patients with regards to renal replacement therapy initiation

Hypothesis

There are sex-specific differences in decision-making of doctors and patients with end-stage renal disease with regards to renal replacement therapy initiation.

Methodology

Questionnaires will be sent to every Austrian chronic kidney disease outpatient clinic willing to participate. Doctors and patients will complete the questionnaire anonymously and questionnaires will be sent back after a 3 months-time period of data collection /questionnaire completion.

The following questions will be included in the questionnaire:

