Doctor level:

In your chronic kidney disease clinic

1. How many men (a) and how many women (b) were registered in the year 2016?
2. According to the first lab result that was taken in 2016, how many men (a) and how many women (b) were in chronic kidney disease stage 4, 3a, 3b, and 2?
3. How many times did the registered men (a) and the registered women (b) have their labs checked and saw the doctor during the year 2016? Please subdivide also by chronic kidney disease stage.
4. How many men (a) and how many women (b) have you informed they will likely need renal replacement therapy (RRT) in the next 12 months?
5. How many men (a) and how many women (b) already have a fistula, and how many have a graft for vascular access?
6. How many men (a) and how many women (b) have you informed about preemptive transplantation as an option for RRT?
7. How many men (a) and how many women (b) have you informed about peritoneal dialysis as an option for RRT?
8. How many men (a) and how many women (b) have you informed about hemodialysis as an option for RRT?
9. How many men (a) and how many women (b) ended up on RRT (HD, PD or preemptive transplantation) during the year 2016?
10. How many men (a) and how many women (b) did you consider end stage and thus in need of undergoing RRT in 2016?
11. How many men (a) and how many women (b) refused RRT in 2016 despite your advice?
12. Among those whom you considered end stage in the year 2016, in how many men (a) and how many women (b) was the decision to withhold or not do RRT mutual (taken by doctor and patient together)?
13. How many men (a) and how many women (b) started RRT in 2016 against your advice?
14. How would you judge your own decision making regarding RRT initiation
 - a) Influenced by patient sex, with men more likely to start RRT
 - b) Influenced by patient sex, with women more likely to start RRT
 - c) Not influenced by patient sex

To obtain adequate data, a reimbursement based on the number of patients seen by the center will be offered to the medical director of the outpatient clinic in December 2016. A specific plan on how to arrive at answering the questions correctly must be submitted; in principle, this plan should encompass several meetings with the outpatient clinic doctors in early 2017, in order to obtain an answer from all of them together (only question 14 must be individually answered).

Patient level:

1. I am a man (a), a woman (b).
2. My age is ... years.

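### The doctor questionnaire in sub-study 3 gives no laboratory count of stage 5 patients by sex and does not split questions 4-13 by stage, so decision differences cannot be cleanly separated from stage mix

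*Combined protocol and SAP*

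**What the plan says.** The hypothesis in section 2.3 reads: "There are sex-specific differences in decision-making of doctors and patients with end-stage renal disease with regards to renal replacement therapy initiation". The German synopsis describes the same target group: "Entscheidungsfindung der Patienten mit terminaler Niereninsuffizienz und der betreuenden Ärzte".

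The doctor questionnaire collects clinic-level counts of men and women.

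- Question 1 asks for the total: "How many men (a) and how many women (b) were registered in the year 2016".
- Question 2 stages patients by their first laboratory result of 2016: "how many men (a) and how many women (b) were in chronic kidney disease stage 4, 3a, 3b, and 2".
- Question 3 asks "How many times did the registered men (a) and the registered women (b) have their labs checked" and how often they saw the doctor, and adds "Please subdivide also by chronic kidney disease stage". It names no stages, and it counts contacts rather than patients.
- Questions 4-9 (RRT information, fistula or graft, information on each modality, RRT starts) and questions 10-13 (end-stage judgement, refusal, mutual decision not to treat, start against advice) are asked by sex, with no laboratory stage.
- Question 10 is the nearest substitute: "How many men (a) and how many women (b) did you consider end stage and thus in need of undergoing RRT in 2016". Question 12 is restricted to that group.

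The patient form is anonymous and has no eGFR or stage item. Only a self-rated end-stage statement comes close. The analysis planned for sub-study 3 is descriptive, with graphs.

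**The concern.** Being told about RRT, having vascular access and starting RRT all become more common as kidney function falls. If the men and women in a clinic differ in stage, the crude proportions differ even when doctors treat both sexes alike at each stage. The sub-study wants to describe differences in decisions, so it needs to see men and women at a comparable stage. Question 2 stops one stage short of the group named in the hypothesis, and the later questions cannot be tied back to stage.

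The protocol itself gives reasons to expect a different mix. In section 1.2, women are 57.7% of those with eGFR 15-29 but 50.6% of those below 15 without dialysis. In section 1.5, awareness in stage 3 without proteinuria is 2.9% in women and 17.9% in men, and the authors link this to women being under-represented in clinics. The first pattern puts relatively more men in the latest stage. The second would remove women from the earlier stages and leave the remaining women with more advanced disease.

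Clinics return aggregate counts, so a missing stage 5 count cannot be rebuilt from the returned forms.

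**Working it through.** Sub-study 3 states no sample size, effect or power, so there is no figure of the plan to reproduce. The check has two parts.

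**1. Can any item replace a laboratory stage 5 count?**

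- Question 1 minus question 2: the remainder mixes stage 5, stage 1 and patients without a usable 2016 result. The plan does not propose it as a denominator.
- Question 3: stage 5 may appear, but only for laboratory checks and visits.
- Question 10: usable for questions 9 and 11-13, but it is a judgement. Section 1.6 raises the possibility that doctors are more reluctant to start RRT in women; such reluctance could also affect whom they call end stage.
- Question 4 and patient item 10: these can partly stratify information on modalities (questions 6-8, patient items 12-14), but being told is also a decision.
- Fistula or graft: factual, but it follows a decision.

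None is a stage count that is independent of the decisions under study.

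**2. Can stage mix alone produce a crude sex difference, and in which direction?**

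Inputs from section 1.2 (Table 3 and text, a US health-care system): female shares of 60.7%, 61.6%, 57.7% and 50.6% for eGFR 45-59, 30-44, 15-29 and below 15 without dialysis. The odds of being below 15 rather than at 15-29 are (0.494/0.506)/(0.423/0.577) = 1.33 times higher in men.

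Assumptions that are not in the documents, both listed in the order of those four eGFR bands:

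- six stage mixes (%): 30/35/30/5, 25/35/30/10, 20/30/35/15, 15/30/35/20, 10/25/40/25, 10/20/40/30;
- six rates of being told that RRT is likely (%), the same in men and women: 1/5/30/80, 0/2/20/80, 0/0/10/90, 2/10/40/80, 5/10/30/60, 0/5/50/90.

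Formula: p(sex) = Σ(mix × share of that sex × rate) / Σ(mix × share of that sex), and OR = odds(men)/odds(women). Equal treatment within stage is built in, so any OR other than 1 comes from stage mix.

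*Worked case, mix 20/30/35/15, rates 1/5/30/80, US shares.* Per 100 patients there are 7.86 + 11.52 + 14.805 + 7.41 = 41.595 men, of whom 0.079 + 0.576 + 4.442 + 5.928 = 11.02 are told (26.5%). There are 12.14 + 18.48 + 20.195 + 7.59 = 58.405 women, of whom 0.121 + 0.924 + 6.059 + 6.072 = 13.18 are told (22.6%). OR = (0.265/0.735)/(0.2256/0.7744) = 1.24.

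*Same case, female odds halved in the two stage 3 bands.* Their female shares fall to 43.6% and 44.5%. Men told 22.6%, women told 25.8%, OR 0.84.

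Over all 36 combinations:

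| Female shares | Crude male-to-female OR | Women in clinic |
|---|---|---|
| US shares | 1.11-1.37 | 56.7-59.6% |
| Stage 3 female odds × 0.6 | 0.81-1.08 (29 of 36 below 1) | 51.4-52.9% |
| Stage 3 female odds × 0.5 | 0.71-1.00 | 48.5-51.5% |

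The text of section 1.2 caps the range at 60.7% although Table 3 shows 61.6%. Using 60.7% for that band changes the first row to 1.10-1.35.

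**The case against.** **The plan contains more stratification than it first appears to.** This stands in part. Question 12 already has an end-stage denominator, and question 10 can serve questions 9, 11 and 13. For modality information, conditioning on having been told removes most of the stage-mix effect. In the worked case with US shares, suppose 50% of told patients below stage 5 and 80% of told stage 5 patients were informed about a modality, in both sexes. Then men are at (0.5 × 5.096 + 0.8 × 5.928)/11.024 = 66.1% and women at (0.5 × 7.104 + 0.8 × 6.072)/13.176 = 63.8%, a ratio of 1.04. What remains exposed is question 4 itself, vascular access and RRT starts.

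**The sizes are assumed.** This stands. Mixes, rates and multipliers are not in the documents. Every clinic in the first row of the table, and 24 of the 36 in the second, has more women than the 40%-52% of section 1.3. Odds ratios also look larger than ratios of proportions: 26.5% against 22.6% is an OR of 1.24 but a ratio of 1.17. The 50.6% share concerns patients without dialysis, a group already shaped by earlier dialysis decisions. Only the possibility of bias in either direction is shown.

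**Laboratory stage is not a neutral yardstick.** This stands as a caveat. Section 1.4 says the sex corrections in creatinine formulas might be wrong, though not by much.

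**The sub-study is descriptive.** It is, and participation is voluntary. That lowers the stakes, but a description still has to show whether men and women at a comparable stage are being compared.

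**Conclusion.** The point holds as a limit on interpretation. Question 2 omits the stage closest to the hypothesis, and questions 4-13 cannot be tied to laboratory stage. Crude sex differences in questions 4, 5 and 9 therefore mix decisions with stage. Under equal treatment within stage, the crude OR was about 1.1 to 1.4 with the protocol's US shares and about 0.7 to 1.1 if women are missing mainly in stage 3. Because the sign can change, no later assumption corrects it. These figures rest on assumed mixes and rates and are not estimates for Austria.

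A reader might infer three stronger things that the documents do not support.

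- That sub-study 3 cannot address its hypothesis at all. Questions 10-13 and the doctors' own assessment in question 14 still describe decisions, although questions 11 and 13 are as unsplit as the rest and need question 10 as denominator.
- That the bias makes women look under-treated. It may do the opposite.
- That question 1 minus question 2 carries a bias of known size. Nothing in the plan says how many patients are in stage 1 or unstaged, and the plan does not use that difference.

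**What to change.** Before distribution:

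- Add to question 2: stage 5 not on RRT, stage 1, and no 2016 result or unstaged, so that the counts sum to question 1.
- Name the same stages in question 3.
- Report questions 4, 5, 9 and 10 by sex next to the stage 4 and stage 5 counts. State that stage is taken at the first 2016 laboratory result and that stage 5 excludes patients who started RRT earlier.
- Tabulate patient items 11-14 by sex within item 10. These are individual forms, so no new data are needed.

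Optional, if questionnaire testing shows that it is feasible: split questions 4, 5 and 9 by stage at the first 2016 result, with cells for stage 5, stage 4, and all other or unstaged, so that totals reconcile. Give questions 4-8 an explicit reference period. Note that patients who progressed during the year stay in their first-result stage, and that the eGFR sex correction may carry some error.

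The cost is three extra counts per clinic, from the staging that question 2 already requires. The optional split may need a look-up in individual records, because the clinic's doctors otherwise meet "in order to obtain an answer from all of them together". Section 3 schedules questionnaire development and testing, when that workload can be tried out.

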3. My nationality is Austrian (a), Non-Austrian (b).
4. My native language is German (a), not German (b).
5. I am married (a), living with my partner (b), separated or divorced (c), single (d), widowed (e).
6. My highest level of education is less than high school.
7. I know the reason (a), don't know the reason (b) why my kidneys are weak or failing.
8. The most important reason why my kidneys are weak or failing, to the best of my knowledge is hypertension (a), diabetes (b), glomerulonephritis (c), polycystic kidney disease (d); another reason not mentioned here (e).
9. I come to the clinic seldom [once a year at the most] (a), frequently [at least 3 times a year] (b) in order to check my labs and/or discuss treatment and progression of my disease.
10. A doctor at this clinic has told me (a) has not told me (b) that I will likely need renal replacement therapy (RRT) within the next 12 months.
11. I already have (a) / don't yet have (b) a fistula or graft for vascular hemodialysis access.
12. A doctor at this clinic has informed me (a) has not informed me (b) about the possibility to undergo pre-emptive transplantation as an option for RRT.
13. A doctor at this clinic has informed me (a) has not informed me (b) about peritoneal dialysis as an option for RRT.
14. A doctor at this clinic has informed me (a) has not informed me (b) about the possibility to undergo hemodialysis as an option for RRT.
 1. I consider myself end stage and thus in need of undergoing RRT within the next 12 months.
15. RRT is not an option for me. I would rather die than go on dialysis.
16. I suffer from nausea/vomiting (a), fatigue/tiredness (b), edema (c), dyspnea (d).
17. I can take care (a), cannot take care (b) of my household.

Methodological Note: The questionnaire will be handed out to all patients coming to the outpatient clinic in the year 2017 by non-medical (administrative) personnel. The number of returned questionnaires will be counted and compared to the number of questionnaires that was handed out. Only the sex of the patient receiving the questionnaire will be recorded. The return of the questionnaire will be anonymous, by placing a box in the patient waiting area.

Statistics:

Data will be entered into an IBM SPSS statistics database. Descriptive analysis and graphical illustrations will be performed.

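### Vascular access is counted by sex but planned modality is not recorded, so a sex difference in access cannot be separated from a sex difference in choosing hemodialysis

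*Combined protocol and SAP*

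**What the plan says.** Sub-study 3 (Section 2.3) uses two questionnaires, and its analysis is descriptive.

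- **Access, doctor form, question 5:** "How many men (a) and how many women (b) already have a fistula, and how many have a graft for vascular access". The question is not limited to patients heading for hemodialysis, to a disease stage or to a date.
- **Access, patient form, item 11:** "I already have (a) / don't yet have (b) a fistula or graft for vascular hemodialysis access". It is put to all respondents, and the form goes to every clinic attender in 2017.
- **Modality, doctor form, questions 6 to 8:** these count patients informed about pre-emptive transplantation, peritoneal dialysis ("have you informed about peritoneal dialysis as an option for RRT") and hemodialysis ("have you informed about hemodialysis as an option for RRT").
- **Modality, patient form, items 12 to 14:** these ask the same of the patient, for example whether a doctor has given information "about the possibility to undergo hemodialysis as an option for RRT".
- **RRT started, doctor form, question 9:** "How many men (a) and how many women (b) ended up on RRT (HD, PD or preemptive transplantation) during the year 2016". The three modalities share one bracket and no split is requested.

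The statistics paragraph names no denominator for access and no stratification by modality.

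**The concern.** A fistula or graft serves hemodialysis, as patient item 11 itself says. A patient heading for peritoneal dialysis or a pre-emptive transplant can only tick option (b) of that item and is then counted with patients who plan hemodialysis but have no access. It is also the only physical preparation asked about: neither form has an item on a peritoneal catheter or a transplant work-up.

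The hypothesis of Section 2.3 concerns sex differences in decisions on starting RRT. The objectives in Section 2 word the same sub-study in terms of hemodialysis initiation. Under either wording, access by sex is a result that readers will look at. It mixes two quantities that a survey of decision-making should keep apart: how many patients of each sex are heading for hemodialysis, and how many of those already have access. The returns are anonymous, so modality cannot be added later.

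**Working it through.** **Step 1. Is planned modality recorded anywhere?** The candidate items are these.

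| Item | What it records | Gives planned modality? |
|---|---|---|
| Doctor 6-8, patient 12-14 | Being informed of each option; one patient can be informed of all three | No |
| Doctor 9 | RRT already started in 2016, modalities pooled | No |
| Doctor 11-12 | Refusal of RRT; mutual decision not to start it | No, only forgoing RRT |
| Patient 15 | Rejection of RRT | No, only rejection |

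No item on either form records it.

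**Step 2. Which denominators are available?** On the doctor form, access can be set against all registered patients (question 1, "How many men (a) and how many women (b) were registered in the year 2016"), those told that RRT is likely (question 4, "have you informed they will likely need renal replacement therapy (RRT) in the next 12 months") or those judged end stage (question 10). The last two bring the base closer to RRT but still mix modalities. The form collects totals, so question 5 cannot be crossed with any other question. The patient form gives individual records, so item 11 can be crossed with item 10, with the unnumbered end-stage statement after item 14 and with item 15. That can set aside patients who reject RRT. It cannot separate hemodialysis from peritoneal dialysis or transplantation.

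**Step 3. What follows arithmetically?** The plan has no figure to reproduce. Assume that access is placed only in hemodialysis planners. Then, for each sex:

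P(access) = P(plans hemodialysis) × P(access given hemodialysis planned)

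All shares below are assumptions. Access among planners is set at 50% in both sexes.

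| Plan hemodialysis, men v women | Access, men v women | Women-to-men ratio | Men-to-women odds ratio |
|---|---|---|---|
| 70% v 60% | 35% v 30% | 0.30/0.35 = 0.86 | (0.35/0.65)/(0.30/0.70) = 1.26 |
| 80% v 70% | 40% v 35% | 0.35/0.40 = 0.875 | (0.40/0.60)/(0.35/0.65) = 1.24 |
| 85% v 80% | 42.5% v 40% | 0.40/0.425 = 0.94 | (0.425/0.575)/(0.40/0.60) = 1.11 |

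When access among planners is equal, it cancels from the ratio, which becomes the ratio of the planning shares. With 80% v 60% the ratio is 0.75 whether access among planners is 40% (32% v 24%), 60% (48% v 36%) or 80% (64% v 48%). With 70% of men and 80% of women planning hemodialysis it is 0.80/0.70 = 1.14, in the other direction. Among planners it is 1.00 throughout.

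**Step 4. Does the choice of base matter?** Shares of 60% to 85% suit a base of patients near RRT, not all clinic patients. Suppose that only 10% of the base is near RRT, equally in both sexes. The 70% v 60% case becomes 3.5% v 3.0%, with odds ratio (0.035/0.965)/(0.030/0.970) = 1.17. The 85% v 80% case becomes 4.25% v 4.0%, with odds ratio 1.07. The ratio of proportions does not change (3.0/3.5 = 0.86).

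**Step 5. Can a real difference be hidden?** Yes. If 70% of men plan hemodialysis and 60% of them have access, the reading is 0.70 × 0.60 = 42%. If 80% of women plan it and 52.5% of them have access, the reading is 0.80 × 0.525 = 42%.

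**The case against.** The case for leaving the forms alone has four parts.

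- **No claim about preparation is planned.** A reader might infer that lower access in women would be reported as poorer preparation. The documents do not say so. They promise descriptive analysis and define no preparation measure. This stands.
- **The forms do address the decision.** A reader might infer that the survey misses its own subject. It does not: doctor questions 9 to 13 count starts, end-stage judgements, refusals, mutual decisions not to start and starts against advice, question 14 asks about the influence of sex, and patient item 15 records rejection of RRT. Modality is one part of the decision, not the whole. This stands.
- **Existing items narrow the gap.** Patient item 15 and doctor questions 11 and 12 deal partly with patients who forgo RRT, and patient item 10 and doctor question 4 bring the base closer to RRT. This also stands. The gap that remains is hemodialysis against peritoneal dialysis or transplantation.
- **Restricting access to planners could lose information.** Planning hemodialysis is itself an outcome of the decision under study. The unrestricted count describes the overall sex difference in moving toward hemodialysis and includes undecided patients who have access. This is a good reason to keep question 5 and item 11 unchanged. It is no reason to leave planned modality unrecorded.

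**Conclusion.** The point holds in a limited form. The forms count access by sex and record no planned or chosen modality, so they cannot show whether a sex difference in access comes from modality choice or from access among patients planning hemodialysis. Equal access overall is no reassurance either.

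The size and direction of any distortion cannot be determined from the documents. On the assumed shares, the women-to-men ratio runs from 0.75 to 1.14 when the ratio among planners is 1.00. These figures rest on invented planning shares, on equal access among planners and on no access outside them. They show what could happen and do not predict a result. A reader might take them as evidence that women will falsely appear less prepared; the documents support neither that direction nor that planned interpretation.

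Because the survey is descriptive and much of it is unaffected, this is a cheap improvement and not a flaw that undermines the sub-study.

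**What to change.** Keep doctor question 5 and patient item 11 as they are, and add the following before distribution.

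- **Doctor form:** among the patients counted in question 4, ask by sex how many currently plan hemodialysis, peritoneal dialysis, pre-emptive transplantation or no RRT, and how many are undecided. Also ask how many of the hemodialysis planners have a fistula or graft.
- **Patient form:** after item 14, add one item on the patient's planned treatment with the same five options plus not yet discussed / not applicable.
- **Analysis:** report access by sex both overall and among hemodialysis planners. Report planned modality by sex as a result in its own right, since it is part of the decision studied.

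The cost is slightly longer forms and some extra counting: five categories by two sexes on the doctor form, plus the access count. Limiting this to question 4 patients spares the clinics from classifying everyone registered. The time table in Section 3 already includes development and testing of the questionnaire. If the items are not added, the report should say that the access comparison cannot be separated from modality choice.
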